- Summary predictor variables as defined by clinicians based on literature (e.g. duration MAP<75, duration HR >100) - different thresholds will be explored
 - **For the primary model, duration MAP<75 will be used (Liem et al.)**
 - Since vitals on the surgical ward may not be measured as frequently, episodes will be defined with the first low value as the start of the event and the first next measurement that is normal as the end of the event.
- Univariate time series (machine learning)
- Multivariate time series (machine learning)

Table 4. Examples of summary variables for vital signs.

These will be modeled based on time stamps as: 1) intraoperative only, 2) postoperative only, and 3) both intraoperative and postoperative periods

Blood pressure	
SBP
 
 1. Maximum decrease from preoperative (defined as median past 24h throughout this table) SBP, as a) absolute change (mmHg), and b) relative change (%) 2. Cumulative duration (minutes) 20% below preoperative preoperative SBP 3. Longest single episode (minutes) below a) 80, b) 90, and c)100 mmHg 4. Cumulative duration (minutes) below a) 80, b) 90, and c)100 mmHg 
MAP
 
 1. Maximum decrease from preoperative MAP, as a) absolute change (mmHg), and b) relative change (%) 2. Cumulative duration (minutes) 20% below preoperative MAP 3. Longest single episode (minutes) below a) 60, b) 65, c) 70, d) 75, e) 80, and f) 85mmHg 4. Cumulative duration (minutes) below a) 50, b) 60, c) 65, d) 70, e) 75, f) 80, and g) 85mmHg
-----------------------	--

Heart rate	
 1. Maximum decrease from preoperative heart rate, as a) absolute change (beats per minute, BPM), and b) relative change (%) 2. Maximum increase from preoperative heart rate, as a) absolute change (BPM), and b) relative change (%) 3. Maximum pulse variation (maximum heart rate minus minimum heart rate) 4. Longest single episode (minutes) below 40, 50, or 60, and above 100, 110, or 120 BPM 5. Cumulative duration (minutes) a) below 60, and b) above 100BPM
Oxygen saturation by pulse oximetry: SpO₂	
 1. Longest single episode (minutes) below a) 88, and b) 90% 2. Cumulative duration (minutes) below a) 88, and b) 90% 3. New postoperative requirement for supplementary oxygen

Other candidate features

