The primary analysis will involve building a linear mixed effects model (with random intercepts) to predict the maximum daily troponin level between postoperative days 0 to 2 as the continuous outcome. The postoperative days 0, 1, and 2 accounts for approximately 40%, 40%, and 10% of MINS, respectively (4). Due to the limitations in retrospective data and the daily troponin monitoring, we will use day as a unit for time rather than hour to avoid overestimation of precision by readers.

For the primary and secondary models described in Objectives 1 and 2, an *a priori* list of predictors will be used: duration hypotension (summarized as a percentage of duration of MAP<75 mmHg in the duration of time modeled, e.g. postoperative day 1) age, sex, emergency surgery, RCRI, and postoperative GFR, as well as the postoperative day and the interaction between postoperative day and % duration MAP<75 mmHg as detailed below.

For longitudinal modeling, the vital signs data and troponin data will be aggregated to the day level, so that the model can predict at the daily temporal level. If there are multiple troponin measurements on the same day, the maximum will be taken. This aggregation of the data is necessary to account for the fact that the vital signs and troponin measurements are measured at irregular intervals (both across patients and data types), often due to the acting physician's response to the patient's condition. Additionally, due to this characteristic of the raw data, the vital signs predictors will be created such that they are standardized to be robust to the number of daily measurements performed (for example, by taking the percentage of day duration, NOT the total duration, of blood pressure below a specific threshold across all measurements during that day). A categorical time variable (representing the day of the measurement) will be included as a predictor within the model.

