Due to the longitudinal nature of the data, we need to include random effects to adjust for the dependence between within-patient daily observations. Thus, at minimum, we intend to include a random intercept corresponding to each patient within the model. However, we may consider including random slopes based on what is observed in the exploratory analysis of the vital signs data, though this would be limited by sample size. Since the effect of a vital signs covariate may be different depending on the day of monitoring, we will investigate interactions between the time predictor and vital signs predictors. This will be performed for only a small number of key time-varying predictors to avoid overfitting, given that the total

number of terms within the model will increase by at least 3 (if the interacting vital signs predictor is continuous or binary) for each additional interaction term included.

Visualizations of the effect of each predictor on the response will also be generated, to further investigate their relationships within the context of the model.

To summarize, a simplified example of the primary linear mixed effects model would be: $\text{Troponin} = \text{intercept} + b1\text{BP_day0} + b2\text{day1} + b3\text{day2} + b4\text{BP_day1*day1} + b5\text{BP_day2*day2} + \text{error}$ (plus other non-BP fixed-effect covariates as listed above). An example interpretation would be $b1$ will correspond to the effect of BP on Day 0, $b4$ will correspond to the additional effect of BP on Day 1 (with respect to Day 0) and $b5$ will correspond to the additional effect of BP on Day 2 (with respect to Day 0). However, we will perform exploratory analysis to explore other forms of longitudinal modeling to select the best model based on discrimination and calibration.

Survival analysis will not be employed due to the small variance in the days for the outcome (days 0-2). Also, right censoring is assumed in survival analysis, which does not apply in our case of troponin rise postoperatively as the majority of patients will not have a troponin increase eventually.

Secondary, Sensitivity, and Exploratory Analyses

In addition to the above outlined primary statistical analysis, we intend to conduct additional secondary, sensitivity and exploratory analyses to address Objectives 2 to 4 to examine how well the model performs given the following changes:

- Introduction of transformations or natural cubic splines on continuous predictors or outcomes

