- Modelling using a generalized linear mixed effects model for binary definitions of troponin increase (per AHA, as described above).
 - Different truncations of vital sign data stream prior to MINS diagnosis (e.g. no truncation, 12h before diagnosis)
 - If sample size allows: subgroup analysis involving only patients with preoperative troponin; subgroup analysis for patients who are in the intensive care unit perioperatively, as this represents a sicker population.
- Intraoperative only, postoperative only
- Further inclusion of additional predictors (e.g. % duration of $\text{HR} > 100$) from the available vital signs data
- Exploration of the incremental value of vital signs in addition to the RCRI or NT-proBNP in predicting MINS or myocardial injury
- Inclusion of information from postoperative day 3
- Delta troponin (change from preoperative troponin) using linear contrast

Model evaluation

To validate the performance of the linear mixed effects model specified in the primary statistical analysis plan, given the longitudinal nature of the data, a repeated patient-based 5-fold cross-validation will be performed with 100 repetitions (doi:

10.1093/gigascience/gix019). Patient-based record was chosen as record-wise cross validation tends to overestimate prediction accuracy compared to subject-wise cross validation. Note that when using a linear mixed effects model to predict troponin for “new”

patients (such as those in a held-out validation set), there are no unique random effects corresponding to those patients and so we are assuming the mean response for these “new” patients. A “patient-based” approach for the cross-validation approach is performed to avoid data leakage from the training set into the validation set (i.e. a patient’s measurements could potentially be present in both the training and validation sets). To quantify predictive performance, the root mean square error (RMSE) will be computed for each repetition, and the corresponding average and standard deviation of those performance measures will be reported. Marginal (i.e. fixed effects only) and conditional (i.e. fixed and random effects) R-squared (Nakagawa and Schielzeth R-squared, doi.org/10.1111/j.2041-210x.2012.00261.x) will be calculated. For assessment of calibration, the predicted values will be averaged across all repetitions (for each actual observation), and a calibration plot will be generated along with measures of the calibration intercept and slope.

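### A performance-selected best model has no validation of the selection step, and nothing keeps the a priori model as the headline; a selected model's AUC may be optimistic

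*Combined protocol and SAP*

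**What the plan says.** Primary Modeling states that for Objectives 1 and 2 "an *a priori* list of predictors will be used". The hypotension summary for the primary model (percentage of time with MAP below 75 mmHg) is fixed there and in the candidate-feature section. After an example model equation, the same section says the team will explore other longitudinal model forms to "select the best model based on discrimination and calibration". On the random-effects structure it adds that "we may consider including random slopes based on what is observed in the exploratory analysis of the vital signs data".

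The candidate-feature section says of the vital-sign summaries that "different thresholds will be explored", and Table 4 lists examples. Objectives 3 and 4 compare hypotension definitions and periods, and ask whether other vital signs add predictive value.

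Model evaluation opens with its target, "To validate the performance of the linear mixed effects model specified in the primary statistical analysis plan", and gives the method: "a repeated patient-based 5-fold cross-validation will be performed with 100 repetitions". RMSE, R-squared and calibration are reported for troponin. The binary models get a similar scheme, with an AUC for each repetition, calibration and decision curves. For these conventional models no inner loop, hold-out set or optimism correction for selection is described. Bootstrap validation appears only under the machine-learning aims.

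**The concern.** The selection sentence sits in the primary modelling section, ahead of the section for secondary, sensitivity and exploratory analyses. As written, a model chosen for its performance could replace the prespecified one in the main report. No passage prevents this, and none says how such a model would be validated.

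A model chosen as the best of several on noisy estimates from one set of patients looks better in those patients than it will in new ones. Splitting by patient prevents leakage of a patient's records between folds, but does not address leakage through selection. The 100 repetitions reduce fold-split noise only, because every repetition reuses the same patients.

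The main risk is to the binary analyses, with about 75 events. Whether vital signs add to existing risk information, and which hypotension definition predicts best, are the study's own questions. Selection can make an uninformative summary appear to help, and the decision curves would carry that forward.

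**Working it through.** **1. The plan's own sizing figures.** With 750 patients and about 75 events:
- Linear mixed model: 750 / 50 = 15 terms, as stated.
- Binary model: 75 / 10 = 7.5, rounded up to 8 variables; 75 / 8 = 9.4 events per variable.

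Both reproduce if the ratios are read as patients or events per parameter. These caps limit the size of a fitted model, not the number of models tried.

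**2. How many candidates there could be.** The plan gives no number. Counting blood-pressure summaries in Table 4:
- SBP: 2 + 1 + 3 + 3 = 9
- MAP: 2 + 1 + 6 + 7 = 16
- Total 25; over three periods (intraoperative, postoperative, both) 25 × 3 = 75.

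This is an upper-end count for blood pressure. Comparing a few model structures would be nearer 3. The simulations therefore cover 3 to 75.

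**3. Binary outcome, 3 to 25 candidates.** Assumptions: 750 patients, 9-10% events, one record per patient, logistic model with 5 covariates plus one candidate, patient-based 5-fold cross-validation with 2 repeats, 120-200 runs per setting. The candidate with the highest cross-validated AUC was kept and tested in 20,000 new patients. Optimism = cross-validated AUC − AUC in new patients. Excess = optimism of the selected model − optimism of a prespecified model in the same data.

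| Candidates | Optimism of selected model | Excess over prespecified |
|---|---|---|
| 3 | +0.004 (SE 0.003) | about +0.007 |
| 10 | +0.006 to +0.017 | +0.011 to +0.019 |
| 25 | +0.016 to +0.031 | +0.019 to +0.029 |

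The ranges span candidate correlations of 0.5 and 0.8 and, for 10 and 25 candidates, a no-signal case with uncorrelated candidates. The prespecified model's own difference was −0.006 to +0.002, so it showed no material optimism.

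**4. Binary outcome, 75 candidates with no true effect.** Assumptions: about 65 to 72 events, 60 or 80 runs per setting. Gain is measured against the covariate-only model; gap = apparent gain − true change.

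| Candidate correlation | Apparent AUC gain | True change | Gap |
|---|---|---|---|
| 0.3 | +0.016 | −0.013 | 0.029 |
| 0.6 | +0.013 | −0.011 | 0.024 |
| 0.8 | +0.009 | −0.008 | 0.017 |
| 0.9 | +0.006 | −0.007 | 0.013 |

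At correlations 0.3, 0.6 and 0.8 the selected model's AUC was overstated by 0.036 (SE 0.005), 0.020 and 0.013. The winner appeared to improve on the covariate model in 82-100% of those runs. Repeat simulations at 0.3 and 0.6 gave apparent gains of 0.015 to 0.023, true changes of −0.013 to −0.015, and overstatement of 0.006 to 0.027.

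**5. Continuous troponin.** Assumptions: 750 patients × 3 days on a log-type scale, a patient random effect in the data, population-level prediction, 3, 10 or 25 candidates, 70-150 runs, tested in 8,000 new patients.
- Excess in R-squared over a prespecified model: +0.001 to +0.005.
- Selected model, cross-validated minus true R-squared: −0.005 to +0.002. The usual slight pessimism of 5-fold cross-validation mostly offsets the selection excess.
- Nested cross-validation minus true R-squared: −0.002 to −0.007, within 0.001 of the same gap for a prespecified model. Nesting removed the selection excess.

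Nested cross-validation was not simulated for the binary outcome.

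**The case against.** The best defence is that the plan already prespecifies what matters. The predictors and the MAP threshold are fixed, and the cross-validation is aimed expressly at the specified mixed model. The selection sentence concerns model structure and calls itself exploratory. The later section frames the alternatives as checks on how the model performs under changes. All of this stands, and it rules out four stronger readings that a reader might infer:

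- **That selection uses the very cross-validated scores later reported.** The plan does not say which estimates drive selection. AUC and calibration measures are described only as cross-validation outputs, so the inference is reasonable, but it is an inference. Selection on apparent measures would need correction too.
- **That the best of 75 summaries will be picked.** The count is right, but Table 4 is headed as examples and no sentence announces such a search. Objective 3 can be met by reporting all definitions without choosing a winner.
- **That the primary troponin result is inflated.** The simulated net effect there is negligible.
- **That the a priori model's validation is compromised.** If reported as specified, it carries no selection optimism.

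Many Table 4 summaries are also near-duplicates (neighbouring cut-offs, overlapping periods), so high correlation, and hence a smaller effect, is plausible for many of them. The documents give no figure.

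The defence does not close the gap. The plan still permits performance-based selection in the same patients, does not say how that step is validated, and does not bar the selected model from becoming the headline.

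**Conclusion.** The concern holds in conditional form. If a performance-selected model is reported from the single-level cross-validation, or from apparent measures, its performance will be optimistic. The exposure is mainly the AUC of the binary MINS models and the apparent incremental value of vital signs (Objectives 2 to 4).

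Simulated AUC optimism is near zero for about 3 candidates and roughly 0.01 to 0.03 for about 10 to 75, with individual settings from 0.006 to 0.036; it shrinks as candidates become more correlated. That is modest in absolute terms, but enough to turn a small true loss into an apparent gain when no candidate has any effect.

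The size rests on assumptions the plan does not settle: number of candidates, their correlation, effect sizes, candidates of equal quality, and one record per patient. Most runs also used 2 repeats rather than 100, which may slightly inflate the excess. The continuous result assumes a log-type scale with well-behaved errors.

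**What to change.** Amend Primary Modeling and Model evaluation to state that:
1. The cross-validated performance of the a priori models for Objectives 1 and 2 is the primary result, whatever the exploration finds.
2. Any model chosen for its performance is labelled exploratory.
3. Performance of a selected model comes only from the outer held-out folds of nested patient-based cross-validation, with every choice (model form including random slopes, threshold, summary, period) repeated inside each training fold.
4. The selection measure is named for each outcome, since the plan defines no discrimination measure for continuous troponin.

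No new data are needed. The cost is a few sentences and computing time. With 5 inner folds, each repetition needs 5 × 5 = 25 inner fits per candidate instead of 5, so reducing the nested runs from 100 to 100 / 5 = 20 repetitions keeps the load about the same, apart from refitting the winner in each outer fold. The reported AUC of a selected model will be slightly less favourable.

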2. To develop and internally validate a model that uses the duration and degree of intraoperative and postoperative hypotension to predict daily probability of MINS or death (binary outcome, according to the 2021 American Heart Association (AHA) definitions (6) from postoperative days zero to two.
3. To evaluate how different definitions of hypotension affect the primary and secondary models above, and analyze the intraoperative and postoperative hypotension separately to determine whether intraoperative or postoperative hypotension alone are sufficient for prediction.
4. To explore whether other intraoperative and postoperative vital sign information (heart rate, oxygen saturation, and end-tidal carbon dioxide derangements at various definitions) add predictive value to the primary and secondary models above.
5. To use machine learning methods to perform exploratory analysis to determine 1) optimal methods for imputation for time series data; 2) visualization of time series data in the setting of prediction; 3) development and internal validation of machine learning models to use the time series data to predict troponin levels; and 4) to determine how many hours earlier than a binary MINS diagnosis were vital signs able

to predict a MINS diagnosis (as determined by when in the time series prior to MINS diagnosis that the model achieved various thresholds of predicted probability).

Methods

This is a single-center, retrospective cohort study on the development and internal validation of a prediction model.

Population

This study will include patients aged 45 years and older undergoing inpatient noncardiac surgery, who had MINS protocol ordered for postoperative high sensitivity troponin monitoring based on the CCS guidelines (5) from January 2020 to June 2021 (estimated sample size of 750, event rate of ~75).

Patients will be excluded if they do not have intraoperative and postoperative vital signs, or any postoperative troponin measurements. Patients who underwent repeat surgery or were readmitted within the first 72 hours postoperatively will be excluded, since patients who are discharged and readmitted will not have vital measurements as outpatients. If a patient had multiple admissions where the MINS protocol was ordered, only the first inpatient admission will be included. Patients who had positive troponin on postoperative day 4 will be excluded, since vital signs are only included up to postoperative day 3 for consistency.

Data sources

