 - a. Nonischemic causes that may be temporally associated (around the time prior to troponin elevation) were individually chart reviewed, and include PE/DVT, sepsis, rapid atrial fibrillation, cardioversion within 24 hours as per the VISION trial (33). Rapid atrial fibrillation will be established as the presence of atrial fibrillation on ECG with a ventricular rate >100 bpm. Sepsis will be defined as the presence of infection and a systemic inflammatory response (SIRS) and per the Third International Consensus Definitions for Sepsis and Septic Shock (Sepsis-3). SIRS requires 2 or more of the following features: core temperature > 38 C or < 36 C; heart rate > 90 beats per minute; respiratory rate > 20 breaths per minute; WBC count $> 12 \times 10^9/L$ or $< 4 \times 10^9/L$ (34).
2. In patients with abnormal baseline troponin values (>14 ng/L) that is considered chronic and stable, postoperative myocardial injury is considered acute if there is postoperatively a $\geq 20\%$ rise in high-sensitivity cTnT, or an absolute increase in high-sensitivity cTnT of ≥ 14 ng/L above preoperative values. If a patient was diagnosed as having preoperative acute myocardial infarction, there must be a decrease in preoperative hsTnT to be considered chronic elevation for this rule to apply. Manual physician adjudication will be performed as a double check.

Note that MINS includes myocardial infarction in the AHA definitions. If a patient died before MINS diagnosis within 3 days postoperatively, this will be considered an event - i.e. the outcome is specifically MINS or death, to avoid competing risk bias due to death. However, we anticipate death within 3 days after surgery to be very rare.

Only the first positive MINS event is included, and hemodynamic data will be truncated up to that point. The MINS “diagnosis time” of MINS vs. no MINS is the first troponin in the serial troponin that fits the MINS criteria, with the start time defined as since the start of the surgery.

The exploratory modeling objectives will model both troponin level and MINS definitions.

Vital sign candidate features (predictors)

- Vital signs time series (SBP, MAP, DBP, HR, SpO2): taken from Surginet (intraoperative) and Cerner (preoperatively on the day of surgery, and postoperative)
 - These will be modeled using time series data from 1) intraoperative only, 2) postoperative only, and 3) both intraoperative and postoperative periods, using the following approaches:

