The Cerner, Surginet, and chart review data will then be linked by de-identified Cerner study ID. The time series time stamps will be shifted to have the start of surgery as 00:00, Jan 1, 2020, in order to standardize the times for longitudinal modeling. Data will then be processed for removal of vital sign artefacts per the Multicentre Perioperative Outcomes Group protocol (35). To generate a final blood pressure dataset, if noninvasive blood pressure and invasive blood pressure are available during the same minute, then the measurement that is 1) not marked as artefact and 2) has a higher systolic blood pressure will be taken. Data will also be processed for calculation of RCRI, determination of the timing of MINS diagnosis, truncation of vital sign time series to the appropriate time stamp (see below), and calculation of duration under threshold of the time series to create vital sign summary variables as described in Table 4 for each postoperative day (0-<24h, 24-<48, 48-<72, and <72-96h after surgery end time). A formal chart review will also be performed to extract data not automatically retrieved from Cerner and Surginet, and verify data quality of automatically extracted comorbidities.

For modeling troponin as a continuous outcome, the vital sign time series will be truncated at the last troponin measurement within 3 days of surgery. For modeling the binary MINS outcome definitions the data will be truncated at the time of troponin laboratory diagnosis of the outcome event, postoperative day 3 (since the MINS protocol monitors for 3 days) or hospital discharge or death, whichever occurs first. All time measurements will be standardized as above in relation to the surgery start time.

Predictive Modeling Approaches

Approach I. Analysis using conventional longitudinal modeling (primary objective)

Data visualization

The initial exploratory analysis of the vital signs and troponin data involves time series visualizations and summaries to explore any potential patterns present in the data that may be associated with troponin quantiles or MINS or myocardial injury diagnosis. Spaghetti plots of the longitudinal data will be created for the outcome and vital signs variables, with lines colour-coded by troponin quantiles or MINS or myocardial injury diagnosis. Other relevant visualizations (scatterplots, boxplots, etc.) examining the associations between the troponin outcome and the vital signs variables will also be created.

Primary Modeling

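### Objective 2's binary GLMM has a weakly identified patient random intercept and no stated rule for new-patient probabilities, so daily MINS/death risk may come out well too low, about right or somewhat too high

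*Combined protocol and SAP*

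**What the plan says.** Objective 2 is to "predict daily probability of MINS or death" over postoperative days 0 to 2. The model is given in one line under Secondary, Sensitivity, and Exploratory Analyses: "Modelling using a generalized linear mixed effects model for binary definitions of troponin increase". The rest of its specification comes from Primary Modeling. The predictor list there applies "For the primary and secondary models described in Objectives 1 and 2", and on random effects the text says that "at minimum, we intend to include a random intercept corresponding to each patient within the model".

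The binary data stop at the event. Outcome states: "Only the first positive MINS event is included, and hemodynamic data will be truncated up to that point". Data processing states: "For modeling the binary MINS outcome definitions the data will be truncated at the time of troponin laboratory diagnosis of the outcome event" (or day 3, discharge or death, if sooner).

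Model evaluation has one sentence on predicting for patients outside the training set. It concerns the linear mixed model for troponin and assigns such patients the mean response, because they have no random effect of their own. For the binary models the section says only that validation will be similar. Predicted probabilities are then averaged over repetitions for a decile calibration plot with intercept and slope, and decision curves are drawn.

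Primary Modeling sets survival methods aside, partly because "right censoring is assumed in survival analysis, which does not apply in our case of troponin rise postoperatively". After the linear example it adds that "we will perform exploratory analysis to explore other forms of longitudinal modeling to select the best model based on discrimination and calibration".

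**The concern.** A random intercept describes how strongly a patient's repeated outcomes go together. Here no patient can have two events: the row pattern is zeros, or zeros ending in a single 1. Such data carry little information on the random-intercept SD. With day terms only, they carry none, because every SD can reproduce the same daily risks. (That case is an illustration; the planned model has covariates, which help partly.)

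In a linear mixed model, setting the random effect to 0 and averaging over it give the same prediction, so the mean-response rule is clear. Under a logit link they differ, and the gap grows with the SD. There is also a third option. Patients still event-free on day 1 or 2 tend to have lower random effects, so the average should be taken over that selected group. The plan does not choose among the three.

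Objective 2 is itself an absolute daily risk, and decision curves compare that risk directly with thresholds. A poorly determined SD combined with an unstated rule therefore affects the main output of this objective.

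**Working it through.** **Figures in the plan.** 750 patients and about 75 events (Population), split about 40/40/10% over days 0/1/2 (Primary Modeling). The parameter limits reproduce: 750/15 = 50 patients per coefficient, and 75/8 = 9.4 events per variable, which the plan rounds to 10. The plan states no random-intercept SD, covariate effect or predicted risk; these are assumed below and shown as ranges.

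**Step 1: at-risk risks.** Events by day: 30, 30, 7.5. Risks: 30/750 = 4.00%, 30/720 = 4.17%, 7.5/690 = 1.09%. Total 67.5 events.

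**Step 2: three rules with the SD known.** Model: logit P(event on day t | event-free, b) = η_t + b, with b ~ N(0, σ²). For each σ, the η_t were solved so that the model reproduces the Step 1 risks exactly. Then:

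- Rule A: expit(η_t), the random effect set to 0.
- Rule B: E[expit(η_t + b)] over N(0, σ²).
- Rule C: the same expectation, with b weighted by Π_{s<t}(1 − expit(η_s + b)), that is, given event-free so far.

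| σ | A: predicted/observed | B: predicted/observed | C |
|---|---|---|---|
| 0.5 | 0.90 | 1.01 | 1.00 |
| 1 | 0.67 | 1.04 | 1.00 |
| 1.5 | 0.44 | 1.10 | 1.00 |
| 2 | 0.26 | 1.18 | 1.00 |
| 3 | 0.08 | 1.38 | 1.00 |

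C is 1.00 by construction. Example at σ = 2: A gives daily risks of 0.88/1.23/0.34%, so (750 × 0.0088 + 720 × 0.0123 + 690 × 0.0034)/67.5 = 17.8/67.5 = 0.26. B gives 4.00/5.15/1.85%, so its excess falls only on days 1 and 2.

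**Step 3: SD estimated, with covariates.** Cohorts of 750 were simulated with cell risks of 4/4/1% and post-event rows removed. The model had 11 coefficients: three day terms, age, sex, emergency, RCRI, GFR and a blood-pressure effect for each day. Assumed absolute log-odds were 0.1-0.2 (weak), 0.2-0.4 (moderate) or 0.35-0.7 (strong), with true SD 0 or 1. Each of the six settings had 120 cohorts, fitted by maximum likelihood with 41-point quadrature and the SD capped at 6. Predictions were for 12,000 new patients.

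| | Weak | Moderate | Strong |
|---|---|---|---|
| Log-likelihood varies by <1.92 over SD 0, 1, 2, 3 | 100% | 87-93% | 50-67% |
| Estimated SD quartiles, true SD 0 | 0/1.33/6.0 | 0/0.15/2.09 | 0/0.23/1.03 |
| Estimated SD quartiles, true SD 1 | 0/1.83/5.83 | 0/0.67/3.01 | 0/1.11/2.08 |
| Rule A below half the true risk | 48-52% | 31-40% | 13-31% |

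Across all settings:

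- Rule A exceeded 0.9 of the true risk in 34-55% of fits. Its medians at true SD 0 ran from 0.56 to 0.91.
- Rule B had medians of 1.07-1.16 and was above 1.2 in 18-46% of fits.
- Rule C and pooled logistic had medians of 0.99-1.02. Pooled logistic was below half in 0 of 720 fits (5th-95th percentile 0.81-1.23).

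A separate simulation with the SD capped at 8 and 60 cohorts per setting found Rule A medians of 0.59, 0.33 and 0.25 at true SD 0, 1 and 2. A 40-cohort run at true SD 1 gave 0.78, so the Rule A median is not a stable summary. A further check (50 cohorts per setting, true SD 0 and 1) found Rule A below half of observed in 38-40% of fits.

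**Step 4: patient-based 5-fold validation.** Moderate effects, 40 datasets at each true SD, 3 repetitions (the plan has 100). Held-out predicted/observed under Rule A was below 0.5 in 38% (SD 0) and 33% (SD 1) of datasets; pooled logistic stayed within 1.00-1.02 (5th-95th percentile). Within one dataset, the 15 training-set SD estimates ran from below 0.5 to above 2 in 53-60% of datasets. The planned averaging over repetitions would mix such fits. The strong-effects run was not completed.

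**Step 5: net benefit at an illustrative 5% threshold.** Per 1000 at-risk person-days, pooled logistic against Rule A (true SD 0; SD 1): weak 2.0 vs 1.0; 1.3 vs 0.7. Moderate 7.0 vs 5.3; 6.2 vs 4.1. Strong 14.0 vs 12.9; 12.7 vs 10.4. The loss is 0.6-2.3 per 1000, or 7-48% in relative terms. At 10% with weak effects there was no loss.

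**The case against.** **The plan's own check would catch the bad cases.** With about 67 events, the standard error of the calibration intercept is roughly 1/√67 = 0.12. Predicted/observed below 0.5 shifts the intercept by about ln 2 = 0.69 or more, over five standard errors. This stands: a severe failure would not be silent. But no consequence is stated for the binary model. The sentence on selecting the best model follows the linear example and names no alternative model or prediction rule for the binary outcome.

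**The large errors belong to one reading.** On the probability scale, mean response could be read as the average over the random effect, where the median excess is modest. This also stands, and is why no single bias figure is claimed. The plan supports either reading.

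**Sizes depend on assumptions.** True. The SD cap of 6 was reached in 4-31% of fits, and a careful analyst might reject such fits. The direction of each rule's error does not depend on the cap, as Step 2 shows.

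**Removal of post-event rows is inferred.** Outcome speaks of truncating hemodynamic data, and a no-truncation sensitivity analysis is listed. Removal is the natural reading of Outcome and Data processing, but it should be confirmed.

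**Stating the prediction rule would be enough.** Rule C performs like pooled logistic, so this is a valid second option. Pooled logistic is simpler and avoids estimating an SD that the data hardly inform.

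**Conclusion.** The concern holds, with high confidence in the structural point: first-event data, a weakly identified random-intercept SD, and no prediction rule that is clear under a logit link. Depending on the rule chosen and the SD that happens to be estimated, daily risk may come out below half its true value, about right, or somewhat too high. If the estimated SD is near 0, the rules agree and nothing is lost.

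The percentages are illustrative. They rest on assumed covariate effects and SDs, on removal of post-event rows, and on a limited number of simulated cohorts. The primary linear model is unaffected. The SAP should be corrected because Objective 2 and its decision curves depend on absolute risk. The stated reasons for avoiding survival methods do not exclude a discrete-time model: patients event-free at the end of follow-up are right-censored, and a few distinct days suit discrete time well.

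**What to change.** For the binary outcome, fit a pooled (discrete-time) logistic regression on at-risk person-days, days 0-2, with the same day terms and predictors, no random intercept, and patient-level resampling. Add one line confirming that rows after the first MINS or death event are removed.

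If the GLMM is kept, state that new-patient probabilities are obtained by integrating over the random intercept conditional on being event-free so far.

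The cost is SAP wording and a simpler model, with no new data. The downside is that patient-specific effects are not estimated for the binary outcome.
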